#### Analysis of all treatment-emergent adverse events

The following TEAEs summaries will be generated for the safety population.

- Overview of TEAEs, summarizing number (%) of patients with any
  - o TEAE;
  - Serious TEAE;

- o TEAE leading to death;
- TEAE leading to permanent treatment discontinuation (patients in usual care treatment arm with no additional LMT are excluded from denominator).
- Number (%) of patients experiencing TEAEs by primary SOC, HLGT, HLT, and PT sorted by the international agreed SOC order and by alphabetical order for the other levels (HLGT, HLT, PT);
- Number (%) of patients experiencing common TEAE(s) presented by primary SOC, HLT and PT (HLT incidence ≥2 % in any treatment group), sorted by internationally agreed SOC order and by alphabetic order for the other levels (HLT and PT);
- Number (%) of patients experiencing TEAEs by primary SOC and PT, sorted by the internationally agreed SOC order and by decreasing incidence of PTs within each SOC (in the alirocumab group). This sorting order will be applied to all other tables of TEAEs by SOC and PT, unless otherwise specified;
- All TEAEs regardless of relationship in one column and, in the same table a second column with TEAEs related to IMP according to Investigator's opinion by primary SOC, HLGT, HLT and PT;
- All TEAEs by maximal intensity (i.e., mild, moderate or severe), presented by primary SOC and PT, sorted by the sorting order defined above;
- The event rate per patient-year (the number of patients with an event in question divided by total patient-years) will be provided for all TEAEs by SOC and PT. For a patient with event, patient year is censored at time of first event; for patient without event, it corresponds to length of TEAE period;
- Kaplan-Meier curves will be provided, when appropriate, for time from first dose of openlabel IMP to the first occurrence of selected TEAEs as well as incidence rates at the time of analysis (Week 24 for the first analysis, Week 32 for the final analysis). Hazard ratio versus usual care group and corresponding 95% CI will be given. Patients without any event will be censored at the end of the TEAE period. Selected TEAEs will be local injection site reactions, general allergic reactions, neurocognitive events, hepatic disorders and TEAE related to any clinically significant signal that needs further characterization.

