#### 8.1.2 Usual care treatment

There are five options available in the usual care arm including the option to add no additional LMT on top of the maximum dose/regimen of statin that is tolerated by the patient or to start one of the following treatments: ezetimibe, fenofibrate, omega-3 fatty acids or nicotinic acid. All patients, regardless of the usual care option that has been selected, should continue on the maximum dose/regimen of statin (non-IMP) that is tolerated by the patient.

The following drugs are identified as IMP:

- Ezetimibe,
- Nicotinic acid,
- Fenofibrate,
- Omega-3 fatty acids

The pharmaceutical form, dose and number of units per administration and timing of dosing of usual care treatment will be determined by the Investigator, and prescribed as per the Investigator's usual practice in accordance with local standard of care.

The usual care IMP will be financially supported by Sanofi. The Investigator will provide the patient with a prescription for usual care IMP at randomization and at Week 12 to cover the treatment period. The commercially available products will be delivered to the patient by the Investigator or other authorized persons (eg, pharmacist) according to the prescription.

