# 1 OVERVIEW AND INVESTIGATIONAL PLAN

### 1.1 STUDY DESIGN AND RANDOMIZATION

This is a multicenter, multinational, randomized, open-label, parallel group stratified study.

After a screening phase of up to 3 weeks, patients will be centrally randomized via interactive voice response system (IVRS) or interactive web response system (IWRS) in a 2:1 ratio to one of the two treatment groups (alirocumab:usual care) and treated for 24 weeks.

Randomization will be stratified by the Investigator's selection of usual care therapy prior to randomization (5 strata: no additional lipid modifying therapy [LMT], or intent to prescribe fenofibrate, ezetimibe, omega-3 fatty acids, or nicotinic acid). Patients randomized to open-label alirocumab will continue on the maximum dose of statin that is tolerated by the patient and will administer alirocumab subcutaneously with a starting dose of 75 mg every 2 weeks for 12 weeks with a blinded up-titration to alirocumab 150 mg every 2 weeks at Week 12 visit if the non-high-density lipoprotein cholesterol (non-HDL-C) at the Week 8 visit is ≥100 mg/dL (2.59 mmol/L). Patients who have a non-HDL-C <100 mg/dL (2.59 mmol/L) at the Week 8 visit will continue with alirocumab 75 mg every 2 weeks until the end of the treatment period. Patients randomized to usual care will follow the option selected by the Investigator prior to randomization. No change during the course of the study will be made to the dose of LMT administered as part of the usual care arm except for nicotinic acid for which the Investigator may prescribe at randomization a scheduled/gradual dose titration in order to allow for the maximum dose to be achieved based on patient tolerability, or except if needed for any usual care LMT for the safety of the patient, based on the Investigator's judgment.

Approximately 420 patients will be recruited and randomized (280 in the alirocumab group and 140 in the usual care group).

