# 2.3.2 Safety population

The safety population considered for safety analyses will be the randomized population who did actually receive at least one dose or part of a dose of the open-label alirocumab and all patients randomized to usual care.

Patients will be analyzed according to the treatment actually received (usual care or alirocumab).

The safety analysis will focus on the TEAE period defined in Section 2.1.4.

In addition:

- Non-randomized but treated patients or patients treated before the randomization will not be part of the safety population, but their safety data will be presented separately;
- Randomized patients for whom it is unclear whether they took the study medication will be included in the safety population as randomized;
- For patients receiving more than one study treatment during the trial, the treatment group allocation for as-treated analysis will be the one to which the patient was treated with the longest duration.

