#### 2.4.5.1 Analyses of adverse events

#### **Generalities**

The primary focus of AEs reporting will be on TEAEs. Pre-treatment and post-treatment AEs will be described separately.

If an AE date/time of onset (occurrence, worsening, or becoming serious) is incomplete, an imputation algorithm will be used to classify the AE as pre-treatment, treatment-emergent, or post-treatment. The algorithm for imputing date/time of onset will be conservative and will classify an AE as treatment emergent unless there is definitive information to determine it is pre-treatment or post-treatment. Details on classification of AEs with missing or partial onset dates are provided in Section 2.5.2.

Adverse event incidence tables will present, the number (n) and percentage (%) of patients experiencing an AE by SOC, HLGT (when applicable), HLT (when applicable), and PT. Multiple occurrences of the same event in the same patient will be counted only once in the tables within a treatment phase. The denominator for computation of percentages is the safety population within each treatment group.

Sorting within tables ensures the same presentation for the set of all AEs within the observation period (pre-treatment, treatment-emergent, and post-treatment). For that purpose, the table of all TEAEs presented by SOC and PT sorted by the internationally agreed SOC order and decreasing frequency of PTs within SOCs (in the alirocumab group) will define the presentation order for all other tables unless otherwise specified. The tables of AEs by SOC, HLGT, HLT, and PT will be sorted by the internationally agreed SOC order and the other levels (HLGT, HLT, PT) will be presented in alphabetical order, unless otherwise specified.

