## Analysis of all treatment emergent serious adverse event(s)

- All serious TEAEs by primary SOC, HLGT, HLT, and PT;
- All serious TEAEs regardless of relationship in one column and, in the same table a second column with TEAEs related to IMP according to Investigator's opinion, by primary SOC, HLGT, HLT, and PT;
- The event rate per patient-year will be provided for all serious TEAEs by SOC and PT;
- All SAEs will be listed.

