# Handling of missing assessment of relationship of adverse events to investigational medicinal product

If the assessment of the relationship to open-label alirocumab/usual care treatment is missing, then the relationship to open-label alirocumab/usual care treatment has to be assumed as possibly related in the frequency tables, but no imputation should be done at the data level.

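### The missing-relationship rule has no exception for usual-care patients who take no IMP, so a blank field counts their events as related to a product they never took

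*SAP*

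**What the plan says.** **Who takes no IMP.** Protocol 8.1.2 states: "There are five options available in the usual care arm including the option to add no additional LMT". The usual-care drugs it then lists as IMP are ezetimibe, nicotinic acid, fenofibrate and omega-3 fatty acids. Protocol 8.2 classes statins as non-IMP background therapy, and Protocol 11.4.3.1 itself refers to statin-only patients as receiving no IMP.

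**Where these patients are counted.** On the usual-care side, the safety population in SAP 2.3.2 has no exposure condition. It takes those who received "at least one dose or part of a dose of the open-label alirocumab and all patients randomized to usual care". For adverse-event tables, SAP 2.4.5.1 (Generalities) says: "The denominator for computation of percentages is the safety population within each treatment group".

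**The relatedness columns.** For all TEAEs the SAP plans, "in the same table a second column with TEAEs related to IMP according to Investigator's opinion". For serious events it plans: "All serious TEAEs regardless of relationship in one column and, in the same table a second column with TEAEs related to IMP". Neither item mentions patients without an IMP.

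**The missing-data rule.** If the relationship assessment is missing, SAP 2.5.2 says "then the relationship to open-label alirocumab/usual care treatment has to be assumed as possibly related in the frequency tables". The data themselves are not altered; the rule acts only in the tables. No group of patients is exempted.

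**A carve-out made elsewhere.** In the TEAE overview of SAP 2.4.5.1, the row for events leading to permanent treatment discontinuation notes that "patients in usual care treatment arm with no additional LMT are excluded from denominator".

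**The concern.** Counting a missing causality assessment as related is a sensible conservative convention when the patient took a study product. It has no such justification when the patient took none. Protocol 10.4.2 asks the investigator for an opinion on whether each event was caused by the IMP or a study procedure. For a statin-only patient there is no IMP to judge, and the documents do not say how the field should be completed. If a site leaves it blank, the SAP rule turns that blank into a related event.

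The problem is one-sided. Every alirocumab patient in the safety population received at least part of a dose, so a blank there is at least an open question about a product taken. Only the usual-care column can contain events called related to an IMP that was never given. Safety and tolerability is a stated secondary objective, and related TEAEs and related serious TEAEs are planned outputs for it. An inflated usual-care column would make alirocumab look relatively better for a reason that has nothing to do with harm.

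**Working it through.** **Base check.** 420 patients at 2:1 give 420 × 2/3 = 280 on alirocumab and 420 × 1/3 = 140 on usual care, as SAP 1.1 states. The documents give no related-event rate, no number of no-LMT patients and no rate of blank fields, so there is no further figure to reproduce.

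**Assumed inputs (not in the documents).**
- s = share of usual care with no additional LMT: 10% to 70%.
- r = share of LMT takers in usual care with at least one related TEAE: 5% to 20%.
- q = share of no-LMT patients with at least one TEAE whose relationship is blank: 0% to 60%.

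**Formulas, on the full usual-care denominator.**
- All no-LMT events entered as not related: r(1 − s). This is the correct arm-level percentage.
- Blank fields counted under SAP 2.5.2: r(1 − s) + qs.
- Excess created by the rule: qs. It does not depend on r.
- Rate among LMT takers only: r. This is a different quantity.

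**Reported usual-care percentage for r = 10%.**

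| s | No-LMT patients of 140 | q = 0 (correct) | q = 10% | q = 30% | q = 60% |
|---|---|---|---|---|---|
| 10% | 14 | 9.0 | 10.0 | 12.0 | 15.0 |
| 30% | 42 | 7.0 | 10.0 | 16.0 | 25.0 |
| 50% | 70 | 5.0 | 10.0 | 20.0 | 35.0 |
| 70% | 98 | 3.0 | 10.0 | 24.0 | 45.0 |

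At s = 30% and q = 10%, for example, 0.10 × 0.70 + 0.10 × 0.30 = 0.07 + 0.03 = 10.0%, so the excess is 3.0 points. At q = 30% it is 16.0 − 7.0 = 9.0 points.

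**Check that r does not matter to the excess.** At s = 30% and q = 30%, r = 5% gives 3.5% rising to 12.5%, and r = 20% gives 14.0% rising to 23.0%. Both differences are 9.0 points.

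**A masking case.** When q = r, the reported figure equals r at every s (the q = 10% column). The table would then match the rate among LMT takers and look plausible, although part of its numerator is false.

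The planned tables are by system organ class and preferred term. The same formula applies row by row, with q for that term, so single rows move by less than the figures above.

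**The case against.** **The field may always be completed.** Protocol 10.4.2 asks for causality on adverse events generally and also covers study procedures. Protocol 10.3.1 to 10.3.4 each say that they do not apply to usual-care patients without an added LMT; nothing similar is said about causality. The natural entry for a statin-only patient is therefore not related, and completion could be near 100%. This stands: the inflation is conditional, and the upper rows and columns of the table are a worst case, not a forecast.

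**A not-related entry is no error.** A reader might infer that the related columns mislead however the field is filled, because no-LMT patients dilute the usual-care rate. The documents do not support that. The comparator is a strategy that includes adding no drug, and a patient given no IMP has no IMP-related event. The figure r(1 − s) is right for the arm; it is only lower than the rate among LMT takers, which the SAP does not claim to estimate here.

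**The discontinuation row as a model.** A reader might also infer that these patients should leave the usual-care denominator, as they do for discontinuation. The SAP gives no reason for that exclusion, and discontinuing an IMP cannot happen to someone who has none. Randomization is stratified by intended usual care, so the alirocumab arm also holds patients whose investigator chose no added LMT. Removing them from usual care alone would set all alirocumab strata against a selected part of usual care.

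**Other tables help.** Safety summaries are descriptive (Protocol 11.4.3, SAP 2.4.5), the column regardless of relationship sits alongside, all SAEs are listed, and safety analyses are repeated by actual stratum. This limits the harm but does not remove the error. Strata are shown only if they hold at least 10% of patients: 14 if that means 10% of 140, 42 if it means 10% of 420, which would be 30% of usual care if only usual-care patients count. The missing-relationship rule would also still apply inside the stratum table.

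**Conclusion.** The point holds for the missing-relationship rule. As written, it gives a false result each time it is triggered in a usual-care patient with no additional LMT, and the error can inflate only the usual-care related columns. The size is q × s and is unknown, because the documents give neither the no-LMT share nor the blank-field rate. Under the assumed ranges it runs from zero (q = 0) to 42 percentage points (s = 70%, q = 60%); 1 to 3 points follow from q = 10% with s between 10% and 30%.

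The documents do not support the stronger claim that the between-arm comparison of related events is wrong in every case, nor the claim that blanks are to be expected. This is a reporting clarification for descriptive tables. No efficacy or confirmatory analysis is affected.

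**What to change.** 1. In SAP 2.5.2, add to the missing-relationship rule: *This rule does not apply to usual-care patients with no additional LMT, for whom relationship to IMP is not applicable; their events are not counted as related to IMP.*
2. In SAP 2.4.5.1, keep the full safety-population denominator in both related-to-IMP columns and add a footnote giving the number of usual-care patients who took no IMP. Keep these patients in the columns that ignore relationship.
3. If a like-for-like view is wanted, use the by-stratum safety tables of SAP 2.4.5, stating how alirocumab patients are assigned to strata, or drop the no-LMT stratum as per IVRS from both arms. Do not drop it from usual care alone.

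The cost is one sentence and one footnote in two tables. No new data are needed. Item 3 is optional and adds output only if requested.

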# Phase 2 and Phase 3 safety results:

Safety data was analyzed from pooled Phase 2 and Phase 3 studies with a Q2W dosing, which included a total of 5234 patients, of which 3340 patients were treated with alirocumab at a dose of 75 or 150 mg Q2W.

In the placebo-controlled and ezetimibe-controlled pooled studies, no dose relationship was noted for any adverse events (AEs) and there was no evidence of a pattern in the type of AEs observed. The percentages of patients who experienced at least 1 treatment emergent adverse events (TEAE), at least 1 treatment-emergent serious adverse event (SAE), and any TEAEs leading to permanent treatment discontinuation were similar between the alirocumab and control groups.

There was no safety signal observed with neurologic events and neurocognitive disorders, alanine aminotransferase (ALT) increase and hepatic disorders, adjudicated CV events, diabetes mellitus, and ophthalmologic disorders in the alirocumab-treated group overall, but more cataracts (2.1%) were noted in patients treated with alirocumab who achieved 2 consecutive LDL-C values <25 mg/dL compared to those treated with alirocumab who did not meet this criterion (0.6%).

The most common adverse reactions in patients treated with alirocumab were local injection site reactions (6.2% patients in the alirocumab group versus 4.2% in control groups in the global pool). Injection site reactions, influenza (upper respiratory symptoms), and pruritus were identified as adverse drug reactions (ADR). Rare and sometimes serious allergic adverse reactions (eg, hypersensitivity, eczema nummular, urticaria, and hypersensitivity vasculitis) have been reported from clinical studies in patients receiving alirocumab.

The analysis of the safety data with Q2W dosing did not suggest a safety signal as of 31 December 2014.

Further details on alirocumab are provided in the Investigator's Brochure.

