#### 8.1.2.1 Route and method of administration

LMT administered as part of the usual care treatment will be taken orally.

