# • Local injection site reactions:

- o deemed to be allergic by the Investigator (or have an allergic component) AND that require consultation with another physician AND related to alirocumab (as opposed to another injectable) AND selected using the following selection of PTs from the safety complementary form for local injection site reaction or from the reported term {"Injection (infusion) site dermatitis", "Injection (infusion) site hypersensitivity", "Injection (infusion) site oedema", "Injection (infusion) site rash", "Injection (infusion) site urticaria", "Injection (infusion) site eczema", "Injection (infusion) site vasculitis", "Injection (infusion) site swelling"};
- o in addition, an analysis will be performed for any local injection site reaction not meeting AESI criteria (not allergic and not requiring consultation with another physician) but meeting the above criteria AND related to alirocumab (as opposed to another injectable).
- Pregnancy of female patient (including male patient's partner) selected using appropriate MedDRA codes.
- Symptomatic overdose with alirocumab:
  - an overdose with alirocumab is defined as at least twice of the intended dose within the intended therapeutic interval (i.e., 2 or more injections are administered in <7 calendar days), to be reported using the term "symptomatic OVERDOSE" (accidental or intentional), indicating the circumstance in parentheses (e.g., "symptomatic overdose [accidental]" or "symptomatic overdose [intentional]"). These events will be selected using the AESI category as selected by the site.
  - in addition, another analysis will be performed analysing all overdose cases (whether symptomatic or asymptomatic) related to alirocumab using the HLT for overdose.

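### The SAP plans a hazard ratio versus usual care for local injection site reactions, but its definition confines that event to alirocumab recipients, so the ratio cannot be estimated

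*SAP*

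**What the plan says.** SAP 2.4.5.1, under the analysis of all treatment-emergent adverse events, plans a time-to-first-event analysis. It opens with "Kaplan-Meier curves will be provided, when appropriate", adds incidence rates at the time of analysis, and continues: "Hazard ratio versus usual care group and corresponding 95% CI will be given". The events are then named: "Selected TEAEs will be local injection site reactions, general allergic reactions, neurocognitive events, hepatic disorders", plus any event tied to a signal that needs further characterization.

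SAP 2.1.4.1 defines two groupings of local injection site reactions. The one of special interest covers reactions judged allergic "that require consultation with another physician AND related to alirocumab (as opposed to another injectable"). The additional grouping covers reactions that miss the special-interest criteria "but meeting the above criteria AND related to alirocumab (as opposed to another injectable"). Both require attribution to alirocumab.

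Protocol 8.1.2 allows usual care to be no added lipid therapy or one of four drugs, and Protocol 8.1.2.1 gives the route: "LMT administered as part of the usual care treatment will be taken orally". The notes to the flow chart in Protocol 1.2 reserve the alirocumab injection at randomization for patients allocated to alirocumab.

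**The concern.** A hazard ratio compares event rates between two groups that are both at risk. Here attribution to one arm's drug is part of the event definition, and the other arm does not receive that drug. A reaction to insulin or any other injectable in a usual-care patient is excluded by the same condition. The contrast is settled by the definition and not by the data.

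What is at stake is the validity of one prespecified table entry. As written, the programmer must report a number that does not exist, or whatever value the software stops at. The SAP gives no fallback here. Its provision for an arm with no responders (SAP 2.4.4.2.3) covers only binary efficacy endpoints.

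**Working it through.** The documents state no figure for this hazard ratio, so there is none to reproduce.

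**Inputs**
- Arm sizes: 280 alirocumab and 140 usual care (SAP 1.1); 420 × 2/3 = 280 and 420 × 1/3 = 140.
- Reaction rate: Protocol section 4 reports "6.2% patients in the alirocumab group versus 4.2% in control groups in the global pool". Applying 6.2% to this trial is an assumption, because the pool covers other studies and the protocol does not say whether attribution to alirocumab was required. The range used is 1% to 10%.
- Usual-care events under the SAP 2.1.4.1 selection, treated per protocol: 0.

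**Step 1: will there be alirocumab events?** Expected number = 280 × p. P(at least one) = 1 − (1 − p)^280.

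| p | expected events | P(at least one) |
|---|---|---|
| 1% | 2.8 | 94.0% |
| 3% | 8.4 | 99.98% |
| 6.2% | 17.4 | over 99.999% |
| 10% | 28 | over 99.999% |

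**Step 2: does the Cox model have an estimate?** Let b be the log hazard ratio, and n1 and n0 the numbers at risk on alirocumab and usual care. With all events on alirocumab, each contributes log[n1·e^b / (n1·e^b + n0)]. This rises with b for every b, so the likelihood approaches a ceiling but never has a maximum. For 17 versus 0 events (simulated event times, censoring at Day 224):

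| b | log partial likelihood | Wald SE of b |
|---|---|---|
| 2 | −96.441 | not computed |
| 5 | −95.355 | not computed |
| 10 | −95.2963 | 50.2 |
| 20 | −95.2959 | 7445 |

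If the software stopped at b = 10, the Wald interval on the log scale would be 10 ± 1.96 × 50.2, or about −88 to 108. The same divergence occurs with 1, 3, 8 or 28 alirocumab events. With 0 versus 0 the likelihood is flat and the ratio is undefined.

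**Step 3: does another interval rescue it?** The SAP does not name the interval type. A profile-likelihood lower limit exists, with no upper limit: about 0.09, 0.56, 1.9, 4.3 and 7.4 for 1, 3, 8, 17 and 28 alirocumab events. With few events the risk sets stay near 2:1, and the limit is close to 0.5 / (e^(1.92/a) − 1) for a events. At a = 17 this is 0.5 / 0.1196 = 4.2, against 4.3 from the actual risk sets. It depends only on the alirocumab count and the allocation ratio, so it carries no comparative information.

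**Step 4: what if one usual-care event does occur?** With 17 versus 1 the hazard ratio is 8.7 (95% CI 1.2 to 66). With 17 versus 2 it is 4.3 (1.0 to 19). One or two exceptional patients fix the result.

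**The case against.** The strongest reply is that the phrase about appropriateness governs the whole bullet, so a sensible programmer would omit the ratio or print it as not estimable. That reading is possible. But the phrase sits with the curves, the sentence on the hazard ratio is unconditional, and the event is listed by name. If omission is intended, the SAP should say so.

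A second reply is that a zero count in usual care is not guaranteed, and this stands in part. The hazard ratio bullet does not itself refer to the SAP 2.1.4.1 selection; that it uses it is an inference, though it is the SAP's main definition of the event. SAP 2.1.4.1 also plans a second selection from the e-CRF drop-down that does not restate the alirocumab condition. SAP 2.3.2 assigns a patient who took both treatments to the one taken longer. The Week 32 call (Protocol 10.1.2.5) allows for a commercial PCSK9 inhibitor started after Week 24. So a reader might infer that the ratio is infinite whatever the drug does, and the documents do not support that. None of these routes makes the ratio interpretable, as step 4 shows.

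A reader might also infer that the placebo training injection always precedes the treatment-emergent period. It need not: Protocol 1.2 marks training at Week 0, and SAP 2.1.4 counts first-day events as treatment-emergent. Such a reaction is still excluded by the attribution condition, but not by its timing.

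Finally, a reader might treat this as a significance test bound to reject. The plan contains no such test: Protocol 11.4.3 rules out formal inferential testing of safety, and SAP 2.4.5 calls the summaries descriptive.

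**Conclusion.** The point holds. Under the SAP 2.1.4.1 selection, with treatment per protocol, the comparator is not at risk. The hazard ratio for local injection site reactions has no finite value or usable Wald interval once any alirocumab event occurs, and is undefined if none does. The divergence does not depend on the assumed reaction rate. The rate affects only how likely at least one event is, and that is 94% or more across 1% to 10%.

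The impact is limited to one descriptive safety output. No efficacy conclusion or alpha depends on it. The listed hazard ratios for general allergic reactions, neurocognitive events and hepatic disorders are unaffected, because their definitions are not tied to alirocumab.

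A reader might expect that removing the ratio would let the trial separate a drug effect from the effect of being injected. It would not: that limit comes from the open-label, oral comparator and remains in any by-arm table.

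**What to change.** Add to SAP 2.4.5.1: for local injection site reactions, no hazard ratio versus usual care is computed; the Kaplan-Meier cumulative incidence in the alirocumab group is given with its 95% CI. Keep the hazard ratio for general allergic reactions, neurocognitive events and hepatic disorders.

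The one-arm estimate would sit beside the summaries already planned in the SAP section on groupings of adverse events: events per injection, time and number of injections to first reaction, intensity and duration. It also moves closer to Protocol 11.4.3.1, which plans Kaplan-Meier curves and 6-month incidence rates for selected events without a hazard ratio.

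The cost is one sentence and one table shell. What is lost is a between-arm number that could not be interpreted.
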